6.2.3 ASSUMPTION CHECKING

Standard model checking will be performed including fitted versus residual plots. Overlap will be checked using minimum and maximum values for each covariate as well as overlap density plots (Markoulidakis, Taiyari, et al., 2021) using the CoBWeb app. Sensitivity analysis plots (using OVtool) (Markoulidakis, Taiyari, et al., 2021; Pane et al., 2021) will be used to assess the assumption of no unobserved confounders left out of the analysis. This could be used even on simple regression analysis, without the use of PS and balancing weights. Alternatively, unmeasured confounding may be assessed using E-values (VanderWeele TJ & Ding P, 2017; Haneuse, et al., 2019).

6.2.4 ALTERNATIVE METHODS IF DISTRIBUTIONAL ASSUMPTIONS NOT MET

TPL/008/2(v1.0)

DOMINO-HD: STATISTICAL ANALYSIS PLAN

If the pseudo-treatment groups, created by the treatment indicators of sleep, diet, and physical activity, are not properly overlapped (Markoulidakis, Taiyari, et al., 2021) at baseline, trimming the sample will be considered. This would be case-specific for each treatment indicator separately. Feasibility of trimming would rely on the missingness rate and the total number of potential outliers compared to the total sample available (e.g. 5% of the total sample could be used as a decision rule as to whether to remove outliers or not).

The HEI and MDI scores will both be used as measures of diet, and binary indicators will be created to split the participants into treatment groups (healthy/unhealthy diet and high/low adherence to MDI, respectively). There is no preference as to which measure is favourable at the time of writing, but one of these could be dropped if either it creates treatment groups with very poor overlap of the baseline covariates (leading to a high rate of outliers), or in case the sizes of the two groups created by the dichotomisation are substantially different e.g. resulting in a 3:1 ratio or more extreme.

6.2.5 SENSITIVITY ANALYSES

OVtool will be used to assess the sensitivity of treatment effect estimation (Markoulidakis, Taiyari, et al., 2021; Pane et al., 2021) to unobserved confounders (for weighted analysis), and to other covariates that could affect the outcome (for unweighted analysis). Alternatively, E-values may be used to assess unmeasured confounding (VanderWeele TJ & Ding P, 2017; Haneuse, et al., 2019).

6.2.6 SUBGROUP ANALYSES

Numbers will not be high enough to conduct subgroup analyses.

6.3 MISSING DATA

Where missing data is likely to occur, it will most likely be due to participant drop-out or loss to follow-up. The amount of missing primary outcome data will be tabulated by pseudo-group and site.

Multiple imputation will be attempted, but the feasibility of this would rely on the sample size and percentage of missingness (>5% of the data points). If the missing rate is below 5%, but the missingness on a specific covariate exceeds 20%, then this covariate could be dropped or replaced, providing an alternative measure is available. If the overall missing rate is below 5%, complete case analysis will be performed.

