4.3 ANALYSIS POPULATION

All participants with available outcome data will be included in the primary analysis. As part of sensitivity analyses, a complete-case analysis (excluding participants with incomplete data) will be performed.

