6. ANALYSIS

6.1 OUTCOME DEFINITIONS

6.1.1 PRIMARY OUTCOME(S)

The primary objective of this study is to establish the feasibility of linking lifestyle, clinical and genetic data and to explore their interplay with HD symptoms and severity.

We will explore the proportions of recruited participants with linked DOMINO-HD and Enroll-HD clinical data as well as linked GWAS data. We will also explore follow-up rates and lifestyle and wearable activity tracker data completeness and balance statistics in important variables. Our data will be used to provide progression criteria recommendations for future studies in this field.

Aspects of feasibility which will be assessed are:

- Completeness of key lifestyle questionnaires (at baseline: HD Pro-Triad, FFQ, LTPA, Sleep, IPAQ, Relationship) data [>80% returned with >80% completeness = feasible, >60% returned with >60% completeness = changes required, <60% returned or <60% completeness = not feasible]
- Completeness of activity tracker data [>70% feasible, 50-70% changes required, <50% not feasible]
- % participants linked with Enroll-HD clinical data [>80% feasible, 60-80% changes required, <60% not feasible]
- % participants linked with GWAS data [>60% feasible, 40-60% changes required, <40% not feasible]
- % participants with follow-up at 12m [>70% feasible, 50-70% changes required, <50% not feasible]
- Feasibility of balancing important covariates. Adequate balance of baseline covariates is achieved when the maximum Kolmogorov-Smirnov (KS) value is equal to or below 0.1. However, as the recommendation is for 60-80 observations per covariate per treatment

TPL/008/2(v1.0)

Centre for Trials Research Canolfan

Ymchwil Treialon

DOMINO-HD: STATISTICAL ANALYSIS PLAN

group (Markoulidakis, Holmans, et al., 2021), the feasibility of achieving balance should be determined alongside the available sample size.

• Agreement between questionnaire and activity tracker data

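### Section 6.3 triggers complete-case analysis by the share of missing data points, so it can discard far more than 5% of participants, and it conflicts with section 4.3

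*SAP*

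**What the plan says.** SAP section 6.3 gives three linked rules.

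- The first makes imputation conditional: "the feasibility of this would rely on the sample size and percentage of missingness (>5% of the data points").
- The second is an optional clause for single covariates: "If the missing rate is below 5%, but the missingness on a specific covariate exceeds 20%, then this covariate could be dropped or replaced". It applies only where a substitute measure exists.
- The third sets the alternative to imputation: "If the overall missing rate is below 5%, complete case analysis will be performed".

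Data points are named only in the first rule. The overall missing rate in the third is not defined separately, and no list of variables is given for its denominator.

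SAP section 4.3 sets the population: "All participants with available outcome data will be included in the primary analysis". It gives complete case a different role: "As part of sensitivity analyses, a complete-case analysis (excluding participants with incomplete data) will be performed".

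**The concern.** The trigger counts cells, but its consequence falls on people. One missing value removes a participant from a complete-case analysis, and no rule in the SAP limits the share of participants lost that way. A model with several variables can therefore pass the 5% test while losing a much larger share of its participants.

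The lifestyle effects would then be estimated in those who wore the tracker and completed the diet questionnaire, with imputation switched off because missingness was judged negligible. The same rule serves every lifestyle-effect model, for cUHDRS and each of its four components.

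The two sections also give different main analyses for the same data. Because the rate has no fixed denominator, the choice between them could be made after the pattern of missing data is known.

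**Working it through.** The 5% threshold is a rule and is not derived from other figures, so there is no calculation in the SAP to reproduce. The check is what the rule permits.

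**Which unit is meant.** The second rule in section 6.3 foresees an overall rate below 5% together with more than 20% missing on one covariate. If the 5% counted participants with any missing value, that could not happen, since the one covariate would already put the rate above 20%. The clause makes sense only if the rate counts cells.

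**Inputs.**
- Model variables, from section 6.2.2: 12-month outcome, its baseline value, the lifestyle factor under study, the other two lifestyle factors, age and HD stage. So k = 7.
- Smaller set, from section 6.2.1, where age and HD stage are added to the balancing only if sample size allows: k = 5.
- Cell rate just under the limit: r = 4.99%.

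**Formulas.** The largest share of incomplete participants is k × r, reached when each has one missing value. If values go missing independently at rate r on every variable, the share is 1 − (1 − r)^k.

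| Variables counted | Maximum incomplete | If independent |
|---|---|---|
| 5 | 5 × 4.99% = 24.9% | 22.6% |
| 6 | 29.9% | 26.4% |
| 7 | 7 × 4.99% = 34.9% | 1 − 0.9501^7 = 30.1% |
| 13 | 64.9% | 48.6% |

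The six-variable row applies if the outcome is left out of the count because it is complete by definition in the section 4.3 population. The 13-variable row is an assumed count: four cUHDRS components at two visits, three lifestyle factors, age and HD stage.

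**Covariates alone, everyone with an outcome.** Assume each of the three lifestyle factors is missing in 11.6% of participants, without overlap.
- Cell rate at k = 7: 3 × 11.6% / 7 = 34.8% / 7 = 4.97%, so complete case applies.
- Participants lost: 3 × 11.6% = 34.8%.
- The 20% covariate clause is not reached, since 11.6% < 20%.

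**One covariate only.** A single covariate missing in exactly 20% gives 20% / 7 = 2.9% of cells. Complete case then drops 20% of participants, and the clause, which needs more than 20%, is still not reached.

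**Clustering.** If two tracker variables (sleep and steps) always go missing together, 17% of participants affected gives 2 × 17% / 7 = 4.86% of cells. The loss is 17%, over three times the nominal 5%.

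**Section 4.3 against section 6.3.** Take a participant with a 12-month outcome and one missing covariate, with the overall rate below 5%. Section 4.3 includes this person in the primary analysis and drops them only in the sensitivity analysis. Section 6.3 drops them from the analysis it prescribes. Below 5%, the sensitivity analysis of section 4.3 therefore repeats the main one.

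**The case against.** Several objections have force.

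- **Drop-out.** The SAP's follow-up criterion is "participants with follow-up at 12m [>70% feasible, 50-70% changes required, <50% not feasible"), so a reader might infer that the 6.3 rule itself throws away the many participants who may lack a 12-month visit. The documents do not support that. Section 4.3 already restricts the analysis to those with an outcome, so these people are outside it under either branch of 6.3. For the same reason, no particular rise in the detectable effect of section 3.3 can be charged to this rule.
- **Table 1 as denominator.** A reader might also infer that the long list of baseline fields in Table 1 enters the missing rate and dilutes it. Section 5.5.2 uses that list for descriptive tables, and nothing says it enters the rate. What stands is only that the set is undefined.
- **The 20% clause.** It does address missingness concentrated in one covariate, and the SAP has substitutes such as IPAQ MET-minutes and self-reported sleep time. But it is optional, works one covariate at a time, and is bypassed in the examples above. Where the covariate is another lifestyle factor with no substitute, using the clause removes a planned confounder.
- **Worst case.** A loss near 35% needs seven variables with missing values spread one per person. Independent missingness on age and HD stage is not realistic, and section 6.3 expects drop-out to be the main cause. This limits the size, but the mismatch of units remains.
- **Importance.** The primary outcomes are feasibility proportions, which no imputation rule changes. Section 6.3 tabulates missing primary outcome data, and section 5.5.2 compares those followed up with those not. This lowers the severity.

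**Conclusion.** The point holds as a defect in the trigger and a conflict between two sections. A cell rate just under 5% is compatible with losing up to about 35% of participants in the seven-variable model. The figure is about 30% under independence, at most about 25% with five variables, and lower when missing values cluster. It can arise from covariates alone among participants with an outcome. These figures rest on the variable counts stated and on assumed patterns of missingness. They show what the rule allows and do not forecast what will happen.

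Bias is not demonstrated. Whether the complete cases differ in a way that matters depends on why values are missing, which the SAP cannot know in advance. What is established is that the 5% test gives no assurance that the loss is small. This should be fixed, but it does not threaten the primary objective, because the analyses concerned are secondary and exploratory.

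**What to change.** In section 6.3, define the trigger as the percentage of participants in the section 4.3 population (outcome available) who have any missing value among the variables of the model in question, and list those variables for each model. If it exceeds 5%, make multiple imputation of covariates the main analysis, with the outcome in the imputation model. Keep complete case as the sensitivity analysis of section 4.3, defined on the same variables. State what is done at or below 5% so that the two sections agree.

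If missing 12-month outcomes are also to be imputed, section 4.3 must be amended to match, because that changes the analysis population.

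The cost is a wording change, made before the analysts see the missing-data pattern. Section 6.6 already lists the imputation software (mice, with MatchThem as an option). The downside is more computing and reliance on missing at random.

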6.4 ADDITIONAL ANALYSES

DOMINO-HD: STATISTICAL ANALYSIS PLAN

DOMINO-HD contains a trial within a study (TWAS), which is investigating methods to improve compliance with use of (and upload of data from) the FitBit trackers using SMS as prompts. This TWAS focuses on the comparison of different strategies of SMS notification sent to the participants, and explores whether any specific strategy resulted in better compliance rates (resulting in more data). The two strategies are characterised by routine and data-driven prompt notifications. Both groups receive an SMS per week, with the message in the first case always the same, while in the latter case it will be more personalised, informed by the success or failure to upload at least 50% of the previous week's data. In both cases, if the data are not updated properly for a certain amount of time, participants receive a phone call after four weeks (routine group), or an enhanced SMS after two weeks (data-driven group).

This is a randomised trial, and the outcome measure will be the total number of wear hours from week two to week nine of participating in the study (the total outcome time frame is eight weeks). Secondary outcomes are the total wear time across the first 3, 6, 9 and 12 months of the study. Statistical testing for difference of means between the two groups will be performed for all outcomes, to understand whether the two approaches lead to different levels of compliance. Two-sided t-tests will be performed to understand if one approach is inferior to the other. Finally, a simple regression model on the average wear hours per week will be fitted to evaluate the effect (if any) of the notification method (including covariates such as age, sex, HD stage, and a dummy variable indicating which group of notifications the participant is in). Descriptive statistics of wear time (in hours) will be reported by group, to examine any patterns of wear over time (decline in total adherence, etc.).

Summary statistics will be reported in a tabulated form, for all outcomes and groups (routine and data-driven), as well as summary statistics and 95% CIs for the mean differences.

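### The randomised SMS sub-study tests weeks 2-9 wear by an unadjusted t-test and does not name week-1 wear as a covariate: lost precision, not bias

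*SAP*

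**What the plan says.** Section 6.4 of the SAP describes a randomised comparison within the study: "The two strategies are characterised by routine and data-driven prompt notifications". Participants in both groups get a weekly SMS. The routine message is fixed, and the content of the data-driven one depends on whether the participant uploaded at least half of the data for the week before.

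For the primary measure, "the outcome measure will be the total number of wear hours from week two to week nine of participating in the study". The later outcomes are cumulative: "Secondary outcomes are the total wear time across the first 3, 6, 9 and 12 months of the study". On testing, "Two-sided t-tests will be performed to understand if one approach is inferior to the other".

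The section then adds that "a simple regression model on the average wear hours per week will be fitted to evaluate the effect (if any) of the notification method". Besides the group indicator, the covariates it gives as examples for this model are age, sex and HD stage. It does not say which weeks that average covers, and it does not name one of the two analyses as the main one.

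Two other places matter. Table 5 (definition of variables/outcomes) lists wear time as measured over the whole study, so week 1 is recorded. Section 6.2.2 has the unweighted regressions for the clinical outcomes control for the baseline value of the outcome.

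**The concern.** An early measurement of the outcome variable, from the same person and device, is often a good predictor of its later value. Here such a measurement exists. Week 1 lies outside the primary window, and message content that depends on the previous week's upload cannot exist until a week has passed. The SAP uses this kind of adjustment for its clinical outcomes but does not name it for its randomised comparison.

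What is at stake is precision. If people differ widely and persistently in how much they wear the tracker, that variation stays in the error term of a raw t-test. The confidence interval for the difference between SMS strategies is then wider than the data require. The planned regression may not remove this variation: its named covariates are demographic and clinical, its list is open, and its window is undefined. Whether week-1 wear is included could therefore be decided after the data are seen.

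**Working it through.** **Is there a figure to reproduce?** No. The SAP gives no sample size, power, standard deviation or target difference for the sub-study. What follows illustrates the possible size of the gain.

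**Inputs from the SAP**
- Significance level 5%, two-sided (sections 4.1 and 6.4).
- Total study size 300-450 (section 3.3).

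**Assumptions**
- All participants are randomised 1:1, so n = 150 per arm at the lower end.
- 80% power, borrowed from the main study for illustration.
- Correlation r between week-1 wear and weeks 2-9 wear of 0.1 to 0.7. The SAP gives no value.

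**Step 1: raw t-test.** The detectable difference in SD units is (1.960 + 0.842) × √(2/n). With n = 150 this is 2.802 × 0.1155 = 0.324 SD. With n = 225 it is 0.264 SD.

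**Step 2: add week-1 wear.** If week-1 wear is unaffected by allocation, adjustment multiplies the variance of the arm difference by 1 − r², and the detectable difference by √(1 − r²). The unadjusted total that would give the same precision is 300/(1 − r²).

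| r | Variance ratio | Variance cut | Detectable difference, N = 300 | Power at 0.324 SD | Equivalent unadjusted N |
|---|---|---|---|---|---|
| 0 (t-test) | 1.00 | 0% | 0.324 SD | 80.0% | 300 |
| 0.1 | 0.99 | 1% | 0.322 SD | 80.4% | 303 |
| 0.3 | 0.91 | 9% | 0.309 SD | 83.6% | 330 |
| 0.5 | 0.75 | 25% | 0.280 SD | 89.9% | 400 |
| 0.7 | 0.51 | 49% | 0.231 SD | 97.5% | 588 |

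**Step 3: check by simulation.** With 4,000 runs at N = 300, the variance ratios were 0.91, 0.77 and 0.51 for r = 0.3, 0.5 and 0.7. Power of the adjusted analysis was 83%, 90% and 98%, against 79-81% for the t-test. This agrees with the formula.

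**Step 4: the comparator.** These figures are measured against the raw t-test. Against the planned regression, the further gain is the squared partial correlation of week-1 wear with later wear, given age, sex and HD stage. The SAP does not give that either.

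**Step 5: the regression's window.** Weeks 2 to 9 are 9 − 2 + 1 = 8 weeks. If the average were taken over those weeks, it would be the primary total divided by 8, and the test of arm would be the same on either scale. The regression can thus become a model of the primary outcome once its window is stated.

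**The case against.** The strongest reply is that nothing here is invalid. Under randomisation the t-test is unbiased, and 95% intervals for the mean differences are planned. An adjusted model is also planned, and its wording, "including covariates such as age, sex, HD stage, and a dummy variable", leaves room for other covariates. The sub-study sits among the additional analyses of a plan that section 4.1.1 calls exploratory, and it has no stated power target to miss. All of this stands. What remains is narrower: the likely strongest predictor is not named in advance, and the adjusted model is neither designated as main nor tied to the primary window.

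A reader might go further and infer that week 1 is an established baseline, free to use. The SAP does not support that. It never calls week 1 a baseline and does not give the timing of randomisation or of the first SMS; both may be stated in a protocol or procedure not seen here. The rule for personalised messages shows only that data-informed content cannot start before week 1 ends. Other contact that differs by arm, or knowledge of allocation, could come sooner. If it changed week-1 wear, adjustment could remove part of the effect. Nor is the change wholly free, since missing week-1 uploads need a rule.

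A reader might also take a gain of a quarter to a half as expected. That rests on r of 0.5 to 0.7, which is assumed. If nearly everyone wears the tracker fully in week 1, that week would vary little and could predict weakly.

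**Conclusion.** The point holds as a matter of efficiency. The SAP tests the primary sub-study outcome without adjustment and does not name week-1 wear, which it records, as a covariate. Against the raw t-test, the variance forgone is 1%, 9%, 25% or 49% at r = 0.1, 0.3, 0.5 or 0.7. It is negligible at the low end and substantial at the high end, and the SAP does not show where the truth lies. The result assumes that week-1 wear is unaffected by allocation; the power figures also assume 1:1 allocation of 300 participants. It would be wrong to read this as bias or as an invalid test. The change is worth making because it is cheap and consistent with how the SAP treats its clinical outcomes.

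**What to change.** In section 6.4:

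1. Make the main sub-study analysis a linear model of wear hours in weeks 2-9 on arm, week-1 wear hours, age, sex and HD stage. Close the covariate list, state the window, and keep the t-test as supportive.
2. Before fixing this, confirm from the sub-study procedure that week 1 precedes any allocation-specific contact. If it does not, use only wear before the first such contact, or omit the covariate.
3. Handle missing week-1 uploads with a missing indicator or imputation. Do not set them to zero automatically, because data not uploaded is not the same as a tracker not worn.
4. For the 3-, 6-, 9- and 12-month totals, exclude week 1 from the outcome whenever it is a covariate, so that the same hours do not stand on both sides of the model.

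The cost is SAP wording, a missing-baseline rule and slightly more analysis work. No new data are needed.

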6.5 HARMS

Safety reporting is covered in the main protocol. Adverse events will be tabulated.

6.6 STATISTICAL SOFTWARE

R version 4.3.0 or higher; R packages: twang, CBPS, entbal will be used to compute propensity scores and balancing weights; R package twang will be used to compute balance statistics (standardised mean difference and KS statistic); R package OVtool will be used to produce sensitivity analysis graphs; R package EValue will be used to calculate E-values; R Shiny app CoBWeb will be used for complete-case analysis (available at: https://[name].shinyapps.io/cobweb/); R package mice will be used for the imputation of missing values; R package MatchThem could be used for missing data analysis; Python version 3.10.2 will be used for the initial extraction of FitBit data.

TPL/008/2(v1.0)

Centre for Trials Research Canolfan

Ymchwil Treialon

DOMINO-HD: STATISTICAL ANALYSIS PLAN

